Recently, real-world evidence data was published from a prospective study in France in which 90 patients treated with a triplet regimen (TPE, IST with corticosteroids and rituximab, and caplacizumab) were compared to a historical cohort of 180 iTTP patients managed with the standard regimen (TPE and corticosteroids, with rituximab as salvage therapy) (24). The primary outcome was a composite of refractoriness and death within 30 days since diagnosis. The composite primary outcome was met for 12.2% of historical patients versus only 2.2% of patients in the triplet regimen met the composite primary outcome of refractoriness and death within 30 days since diagnosis ($p=0.01\%$). The study also confirmed the effect of caplacizumab on the prevention of exacerbation: a significant decrease in exacerbations was noted in the triplet regimen cohort compared to the historical cohort (3.4% vs. 44%, $p<0.01$). Patients in the triplet cohort showed durable platelet recovery 1.8 times faster than historical patients (95% confidence interval [CI], 1.41-2.36, $p<0.01$), and required fewer TPE sessions (5 days vs. 10 days, $p<0.01$). After a median follow-up of 127 days (range: 47-200 days), only one clinical relapse (1.1%) occurred in the triplet regimen cohort (patient with ADAMTS13 <10% at time of stopping caplacizumab) suggesting that it is possible to decrease disease recurrence when caplacizumab is given until the underlying disease is controlled.

In addition to the benefits provided by caplacizumab with immunosuppression and TPE regimen as above, the proposed caplacizumab regimen is expected to provide additional direct benefits to iTTP patients. As the regimen does not include first-line TPE, there will be decreased treatment-related burden with reduction in TPE-related complications including procedural complications (invasive catheter placement and associated AEs such as bleeding, thrombosis, infections, pneumothorax) and plasma related complications such as allergic reactions including anaphylaxis, serum sickness, hypotension requiring dopamine). In addition, this caplacizumab treatment regimen will decrease the health care related financial impact on the patient and improve quality-of-life due to decreased burden of care (relative to caplacizumab with first-line TPE) and increase patient satisfaction with treatment.

This regimen will also result in a reduction in iTTP-associated healthcare resource utilization (HCRU).

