Study participants will not receive TPE as first-line therapy. However, participants may receive TPE if it is determined that there is lack of adequate response to treatment after first 24 hours or if there is any clinical deterioration at any time during the study, including during the first 24 hours (please see below for additional details). It is expected that the participant is hospitalized when the treatment is started, and the duration of initial hospitalization may vary based on clinical condition of the individual participant.

Caplacizumab treatment will be continued until sustained ADAMTS13 activity level of $\geq 50\%$ at 2 consecutive visits after platelet count normalization (defined as $\geq 150 \times 10^9/L \times 2$ consecutive values) or 12 weeks, whichever occurs first. Thus, the maximum treatment duration of caplacizumab will be 12 weeks for the presenting episode.

The post-treatment follow-up period will be 12 weeks. The anticipated study duration per participant without a recurrence while on therapy is maximum of approximately 24 weeks (ie, approximately 1 day for screening + maximum 12 weeks of treatment for the presenting episode + 12 weeks of follow-up).

Initial treatment regimen during hospitalization:

1. anti-vWF therapy: Caplacizumab

Recommended dose: Caplacizumab 10 mg (11 mg in US and Canada; see [Section 2](#)) intravenous (IV) for a single dose followed by caplacizumab 10 mg (11 mg in US and Canada) subcutaneous (SC) 4-6 hours after the IV dose (Day 1) (exceptions to this are detailed in [Section 1.3.4](#)). This will be followed by caplacizumab 10 mg (11 mg in US and Canada) SC daily starting on Day 2 for a maximum treatment duration of 12 weeks.

Note: The baseline ADAMTS13 activity level results from the local laboratory, available within 48 hours will be used to confirm the diagnosis of iTTP. It is expected that there will be minimal discrepancy between local and central laboratory ADAMTS13 activity levels. The central laboratory test results will be available only after 3-4 days.

- If the baseline central laboratory ADAMTS13 activity is <10% of normal → continue caplacizumab and IST.
- If the baseline central laboratory ADAMTS13 activity is between 10% - 20% of normal → use clinical judgment in deciding to continue or stop caplacizumab treatment after evaluation of the totality of signs and symptoms plus other laboratory data.

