- If there is persistent thrombocytopenia, defined as lack of a sustained platelet count increment or platelet counts of $<50 \times 10^9/L$ and a persistently raised LDH level ($>1.5 \times$ upper limit of normal [ULN]) despite five days of treatment.
- If there is clinical evidence of new or progressive ischemic organ injury (worsening of presenting signs and symptoms or appearance of new signs and symptoms such as but not limited to neurologic manifestations [seizures, sudden onset numbness or weakness of the face, arm, or leg especially on one side of the body, mental status changes including confusion, trouble speaking, or understanding speech, sudden visual impairment, sudden difficulty walking, loss of balance or coordination, sudden severe headache with no known cause], cardiac manifestations such as chest pain with or without electrocardiogram (ECG) changes suggestive of myocardial ischemia, increasing troponin, renal manifestations such as worsening serum creatinine at any time after starting therapy, TPE may be started at Investigator discretion at any point during the study, including the first 24 hours and cplacizumab and IST continued.

If participant needs TPE:

Recommend TPE with plasma (eg, fresh frozen plasma, solvent detergent/viral-inactivated plasma, cryosupernatant) at 1 to $1.5 \times$ estimated plasma volume. TPE should be performed daily according to standard site practice and continued at least for 2 days after the platelet count normalization ($\geq 150 \times 10^9/L$). Of note, TPE with 1 to $1.5 \times$ estimated plasma volume may be spread over multiple sessions within 24 hours. Tapering of TPE after platelet count normalization, defined as reducing its frequency to less than once per day, is strongly discouraged and if considered, should be discussed with the Medical Monitor.

Treatment plan for continued therapy with cplacizumab and IST regardless of hospitalization status:

If there is response to initial therapy:

- The participant will continue cplacizumab 10 mg (11 mg in US and Canada) SC daily until sustained ADAMTS13 normalization ($\geq 50\%$) at 2 consecutive visits after platelet count normalization defined as $\geq 150 \times 10^9/L$, or for 12 weeks, whichever occurs first. The maximum treatment duration of cplacizumab is 12 weeks for the presenting episode.

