- Post-treatment medications are those the participant took in the period running from the end of the concomitant medications period up to the end of the study.

A given medication can be classified as a prior medication and/or as a concomitant medication and/or as post-treatment medication. If it cannot be determined whether a given medication was taken prior or concomitantly or post, it will be considered as prior, concomitant, and post-treatment medication.

The prior and concomitant and post-treatment medications will be summarized for the mITT population by anatomic and therapeutic level. The summaries will be sorted by decreasing frequency of Anatomical Therapeutic Chemical (ATC) category. In case of equal frequency, alphabetical order will be used. Participants will be counted once in each ATC category (anatomic or therapeutic) linked to the medication. Corticosteroids and anti-CD20 antibody treatments will be described through summaries.

In addition, all TPE will be described using the following variables: number (%) of participants requiring TPE, reason, time since first caplacizumab administration defined by date of TPE – date of first administration of caplacizumab (whatever marketed or study IMP) + 1 day (days), plasma product name, donor specification, plasma exchange technique, amount of plasma exchanged, multiple of plasma volume to be exchanged, and number of sessions for the desired plasma volume.

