- with or without clinical evidence of new or progressive ischemic organ injury, within 30 days of stopping TPE or anti-vWF therapy.

Clinical Relapse:

Clinical relapse is defined after a Clinical Remission as:

- platelet count decreases to $<150 \times 10^9/\text{L}$ (with other causes of thrombocytopenia excluded)
- with or without clinical evidence of new ischemic organ injury
- confirmed by documentation of severe ADAMTS13 deficiency ($<10\%$)

Number of hospitalization (including hospital and ICU) days during the on-treatment period and during the overall study period

$$\sum_{1}^{x} (\text{Date of Discharge for hospitalization } X - \text{Date of Admission for hospitalization } X + 1)$$

Number of days in ICU during the on-treatment period and during the overall study period

$$\sum_{1}^{x} (\text{Date of Discharge in ICU } X - \text{Date of Admission in ICU } X + 1)$$

Number of TPE days (if participants started TPE) during the on-treatment and during the overall study period

Number of TPE days will be equal to the number of TPE occurrences/observations in the database during the respective periods.

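### Hospital and ICU days are summed over whole stays with no cut at the period limits, and the record that counts as a TPE day is not defined

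*SAP*

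**What the plan says.** SAP Section 5.4 (Appendix 4) defines three measures of care use, each for two periods.

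- **Hospital days.** Under the heading "Number of hospitalization (including hospital and ICU) days during the on-treatment period and during the overall study period", one formula is given: the sum over stays of discharge date minus admission date plus 1.
- **ICU days.** Under "Number of days in ICU during the on-treatment period and during the overall study period", the same formula is applied to ICU stays.
- **TPE days.** "Number of TPE days will be equal to the number of TPE occurrences/observations in the database during the respective periods".

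SAP Section 3.1 starts both periods at the first caplacizumab administration, marketed or study. The on-treatment period ends at the last administration and the overall study period at the end of the study.

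The protocol supplies the context. Section 4.1 states: "It is expected that the participant is hospitalized when the treatment is started". Section 1.3.1 (footnote e) has sites record hospital and ICU admission and discharge dates for the current hospitalization from screening onward. Section 4.1 also allows that a TPE of the planned volume "may be spread over multiple sessions within 24 hours". SAP Section 5.3, in listing what will be described for TPE, includes "multiple of plasma volume to be exchanged, and number of sessions for the desired plasma volume".

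**The concern.** The headings promise days within a period, but the formula returns the length of whole stays. Three things follow if it is programmed as written.

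1. Days from admission to first dose enter periods that begin at first dose.
2. A stay that runs past the last dose is credited in full to the on-treatment period.
3. Adding 1 per stay counts a date twice when one stay ends and the next begins on that date.

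The text also does not say which stays enter which period's sum, or what to do with a stay still open at the end of the study.

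The TPE rule raises a separate question of unit. It equates days with database records, but neither document says whether a record is a session, an exchange or a day.

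Protocol Section 2.3.2 names ICU days, length of hospital stay and the amount of plasma exchange among the burdens the regimen should reduce. In a single-arm trial such figures can be read only against external ones, so the counting unit has to be clear.

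**Working it through.** The documents give no planned or expected value for hospital, ICU or TPE days, so there is no figure to reproduce. The check applies the SAP formulas to assumed records and compares them with a count of distinct dates inside the period. Day 1 is the day of first dose.

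**1. Days before the first dose**

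Inputs: discharge on Day L; admission *a* days before first dose. Both are assumed. The protocol limits screening to 2 days and lets it fall on Day 1, so *a* = 0, 1 and 2 are shown. It sets no limit on how long before screening a patient may have been admitted.

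SAP count = L + a. Count cut at first dose = L. Overcount = a / L.

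| Discharge | a = 0 | a = 1 | a = 2 | Cut at first dose |
|---|---|---|---|---|
| Day 7 | 7 (0%) | 8 (1/7 = +14%) | 9 (2/7 = +29%) | 7 |
| Day 10 | 10 (0%) | 11 (1/10 = +10%) | 12 (2/10 = +20%) | 10 |
| Day 14 | 14 (0%) | 15 (1/14 = +7%) | 16 (2/14 = +14%) | 14 |

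**2. A stay that crosses the last dose**

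Assumed: admission Day 80, last dose Day 83, discharge Day 87.

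- SAP formula, either period: 87 − 80 + 1 = 8.
- Cut at last dose, on-treatment: 83 − 80 + 1 = 4.
- Overall study period: 8, unchanged.

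**3. A date shared by two stays**

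Assumed: ICU stays on Days 1 to 3 and Days 3 to 5.

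- SAP formula: (3 − 1 + 1) + (5 − 3 + 1) = 6.
- Distinct dates: 5.

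**4. TPE days**

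Assumed: 5 true exchange days, of which a share *f* is split into two sessions.

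- One record per exchange: 5 records, overcount 0%, whatever *f* is.
- One record per session: 5 × (1 + f) records, so 6.25, 7.5 or 10 for f = 25%, 50% or 100% (+25%, +50%, +100%).

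Which line applies depends on the layout of the Plasma Exchange form, which is not in the documents. The session count listed in SAP 5.3 reads as a field describing an exchange, which favors the first line. Either way, only participants who receive TPE are affected: at the planning rate of 18%, 0.18 × 55 = 9.9, or about 10 of the 55. Because the TPE count is limited to records within each period, the pre-dose problem in step 1 does not apply to it.

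**The case against.** **The headings already restrict the count.** Each says the days are those during a named period, and SAP 3.1 defines the periods, so a programmer may well truncate. This is fair as to intent. But the formula is the operational definition, it contains no cut, and Section 5.4 writes time limits out where it wants them, as for the daily laboratory windows. The clarification is still needed.

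**Split exchanges.** A reader might infer that they inflate TPE days, even to the size of the contrast cited in protocol 2.3.2 ("required fewer TPE sessions (5 days vs. 10 days"). The documents do not support that. It needs every exchange to be split and every session to be its own record, and SAP 5.3 points the other way. The cited contrast itself mixes sessions and days, and the visible SAP plans no comparison with it.

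**Equal on-treatment and overall totals.** A reader might take equal totals for the index stay as a sign of error. They are not. Caplacizumab continues after discharge for up to 12 weeks in all, so an index stay that ends before the last dose gives equal totals under a truncated count as well. Only a stay that crosses the last dose is affected.

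**The size may be zero.** Screening and first dose can fall on the same day, treatment is meant to start promptly, and the period begins at a marketed pre-study dose where there was one. This stands, so every range above starts at 0%.

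**Hidden rules.** The sections on other endpoints are blacked out and could hold further detail. This also stands. The point concerns the rule as it appears in Section 5.4.

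**Direction.** Each overcount raises apparent care use, so it works against the claimed benefit and cannot create a favorable result. This stands and limits the importance of the point.

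**Conclusion.** The hospital and ICU rule, as written, does not deliver the quantity its headings name. It adds any pre-dose days to both periods, adds days after the last dose to the on-treatment period, and counts shared dates twice. On the assumed stays, the pre-dose overcount is 0 to 29% for discharge on Day 7 and 0 to 20% for discharge on Day 10. The assumed stay across the last dose doubles the on-treatment count, 8 against 4. The true size depends on admission dates that the documents do not give, and it would be larger if patients were admitted more than 2 days before dosing.

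For TPE days the finding is only that the unit is undefined; an overcount is possible but not shown.

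Severity is low. All analyses are descriptive, and none of these counts feeds the primary endpoint or a listed secondary endpoint.

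**What to change.** Replace the three derivations in SAP Section 5.4 with date-based rules.

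- **Hospital and ICU days:** the number of distinct calendar dates in the union of the participant's stays, each cut to run from the later of admission and period start to the earlier of discharge (or death) and period end. A stay still open is counted to the period end.
- **TPE days:** the number of distinct calendar dates in the period with at least one TPE record. Report the number of sessions separately.

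The TPE rule handles repeated records on one date without having to settle whether a record is a session or an exchange. The cost is about two sentences in the SAP and simple programming, using dates already collected.
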